6.1.2. Analysis of the Primary Efficacy Endpoint

The CR rate at Week 25 and the corresponding 2-sided 90% exact CIs based on Clopper-Pearson method will be presented.

6.2. Secondary Efficacy Endpoints

The secondary efficacy endpoints are:

- Rate of CR with MRD negativity ($<10^{-4}$) in bone marrow (CR/BM MRD-) at Week 25, defined as the proportion of subjects who achieved CR/CRi and also achieved BM MRD negativity at Week 25
- Rate of CR with MRD negativity ($<10^{-4}$) in peripheral blood (CR/PB MRD-) at Week 25, defined as the proportion of subjects who achieved CR/CRi and also achieved PB MRD negativity at Week 25
- Overall response rate (ORR) at Week 25, defined as the proportion of subjects who achieved CR, CRi, partial response (PR), or PR with lymphocytosis at Week 25

The response assessment definition of each response category is based on Modified IWCLL 2008 criteria and PR includes nodular partial response (nPR).

The MRD response is assessed with four-color-flow cytometry (FACS) and MRD negativity is defined as one CLL cell per 10,000 leukocytes [0.01 %], ie, $<10^{-4}$.

The analysis window of Week 25 response assessment is defined as $24 \times 7 \pm 28$ days (inclusive) starting from first dose. If there are multiple assessments within the analysis window, records will be chosen based on rules specified in Section 3.8.3.

6.2.1. Rates of CR/BM MRD- and CR/PB MRD- at Week 25

Subjects who received anti-cancer therapy other than the study drug prior to achieving CR with MRD negativity at Week 25 will be considered as nonresponders and will be included in the denominators of the response rates.

The rates of CR/BM MRD- and CR/PB MRD- and the corresponding 2-sided 90% exact CIs based on Clopper-Pearson method will be presented.

6.2.2. ORR at Week 25

When calculating ORR at Week 25, subjects who received anti-cancer therapy other than the study drug prior to achieving responses at Week 25, will be considered as nonresponders and will be included in the denominator.

ORR at Week 25 and the corresponding 2-sided 90% exact CIs based on Clopper-Pearson method will be presented.

A by-subject listing of overall response based on modified IWCLL 2008 criteria will be provided.

A by-subject listing of BM and PB MRD results will be provided.

CCI [REDACTED]

[REDACTED]

[REDACTED]

[REDACTED]

[REDACTED]

[REDACTED]

[REDACTED]

[REDACTED]

[REDACTED]

[REDACTED]

[REDACTED]

[REDACTED]

[REDACTED]

[REDACTED]

[REDACTED]

[REDACTED]

CCI [REDACTED]

[REDACTED]

[REDACTED]

[REDACTED]

6.4. Change From Protocol-Specified Efficacy Analyses

As understanding of clinical response and response per modified IWCLL 2008 criteria beyond week 25 are desired, the following endpoints not defined by protocol will also be analyzed:

- ORR, defined as the proportion of subjects achieving best overall response of CR, CRi, PR, or PR with lymphocytosis per Modified IWCLL 2008 criteria while on study
- Time to clinical response, defined as the interval from first dose of study drug to the date of the first clinical response which includes clinical complete response (CCR) and clinical partial response (CPR)

[REDACTED]

Clinical response assessment is a qualitative treatment response assessment based on physical exam, laboratory parameters and presence of B-symptoms performed every 4 weeks until Week 33 Day 1 and then at all scheduled visits thereafter following the modified IWCLL 2008 criteria, with the exception of lymphadenopathy, hepatomegaly, splenomegaly, and bone marrow. Clinical response categories are CCR, CPR, stable disease, and suspected progressive disease.

The date of disease progression will be the time point at which progression is first identified by relevant radiographic imaging data or clinical data.

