1.2. Study Design

This is a Phase 2, prospective, open-label, multicenter trial to evaluate the safety and efficacy of the combination of tirabrutinib and idelalisib with and without obinutuzumab in subjects with relapsed or refractory CLL.

Eligible subjects will be randomized in a 1:1 manner to one of the following two arms, stratified by the presence of 17p deletion/TP53 mutation (del17p/TP53mut) in CLL cells:

- Arm A: tirabrutinib + idelalisib
- Arm B: tirabrutinib + idelalisib + obinutuzumab

With Amendment 3, randomization was discontinued. All subsequent subjects will be enrolled into Arm B.

Duration of Treatment:

Tirabrutinib 80 mg and idelalisib 100 mg will be self-administered orally once daily. Dosing of both agents will begin on Week 1 Day 1 of the study and thereafter continue for up to 104 weeks in the absence of disease progression, unacceptable toxicity, or documentation of complete remission (CR) with bone marrow minimal residual disease (MRD) negativity (CR/BM MRD-). If CR/BM MRD- is documented on study, treatment will stop after the earlier of:

- i) an additional 3 months of therapy or
- ii) 104 weeks of total treatment.

Obinutuzumab will be administered as 8 intravenous infusions of 1000 mg each over 21 weeks. A test dose of 100 mg will be administered on Week 1 Day 1. If this dose is tolerated, the remainder of the full dose may be subsequently administered on Day 1. Alternatively, the remaining 900 mg will be administered on Day 2. Subsequent infusions will be administered on Week 2 Day 1, Week 3 Day 1, Week 5 Day 1 and then every 4 weeks through Week 21.

This study will continue to monitor subjects for up to 30 days post end of treatment, or up to Week 25 should a subject discontinue treatment prior to Week 25 for reasons other than disease progression.

Efficacy Assessment Schedule:

Tumor response assessment per modified International Workshop on CLL (IWCLL) 2008 criteria will be performed at the Week 25 visit, with evaluation of areas affected by CLL during the screening evaluation. During the treatment phase, additional response assessment per IWCLL 2008 criteria may be performed as clinically indicated.

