Clinical response based on physical exam, laboratory parameters and presence of B-symptoms will be performed every 4 weeks until Week 33 Day 1 (except for Week 25) and then every 12 weeks starting Week 33 until Week 105 following the modified IWCLL 2008 criteria, with the exception of lymphadenopathy, hepatomegaly, splenomegaly, and bone marrow.

Bone marrow MRD will be assessed at Week 25. Additional bone marrow MRD may be assessed as clinically indicated. Peripheral blood MRD will be assessed on Day 1 of Weeks 1, 13, 25, 33, 45, 105, and End of Treatment (EOT). EOT collection is not needed for subjects who complete the Week 105 visit.

The Schedule of Assessments is located in [Appendix 1](#).

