6.4.1. ORR

The analysis will be performed with data collected throughout the study. Subjects, who never achieved these responses or received anti-cancer therapy other than the study drug prior to achieving responses, will be considered as nonresponders and will be included in the denominator when calculating ORR.

ORR and the corresponding 2-sided 90% exact CIs based on Clopper-Pearson method will be presented. A by-subject listing of overall response will be provided.

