6.4.2. Time to Clinical Response **CCI** per Clinical Response Assessment

Time to clinical response in months will be calculated by $(\text{date of first clinical response} - \text{date of first dose of study drug} + 1) / 30.4375$.

Time to clinical response will be summarized using descriptive statistics. A by-subject listing of time to clinical response will be provided.

CCI
[REDACTED]

CCI

For missing or incomplete dates of new anti-cancer therapy and death, imputation rules are described in Sections [6.3.2](#) and [6.3.1](#), respectively.

CCI

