- 14 CLL immunophenotyping, karyotyping and FISH, TP53 and IgHV mutation status, CD38 and ZAP70 expression will be evaluated from peripheral blood at screening. In the event of disease progression, only FISH and TP53 will be evaluated.
- 15 Tumor evaluation by CT scan (preferred) or MRI of neck, chest, abdomen, and pelvis will be performed at screening (unless scan was already completed up to 42 days prior to first dose). At the Week 25 visit, the same type of evaluation should be performed on those body regions which showed involvement by CLL at screening. An additional CT may be obtained on protocol per investigator discretion following evidence of an improvement in clinical response if the response assessment at the Week 25 visit is less than a complete response or in the event of suspected disease progression.
- 16 A bone marrow evaluation is required in the screening window for subjects without radiographic evidence of disease. Bone marrow aspirate and biopsy should be performed at Week 25 for subjects fulfilling clinical response criteria for CR or CRi per the modified IWCLL 2008 criteria. MRD should be assessed from bone marrow aspirate at the reference laboratory in Kiel; CCI
- CCI
- 17 Qualitative treatment response assessment based on physical exam, laboratory parameters and presence of B-symptoms should be performed every 4 weeks until Week 33 Day 1 and then at all scheduled visits thereafter following the modified IWCLL 2008 criteria, with the exception of lymphadenopathy, hepatomegaly, splenomegaly, and bone marrow. Assessment of response per modified IWCLL 2008 criteria should also be recorded at the completion of 24 weeks on treatment and subsequent to any CT and/or bone marrow biopsy that is repeated while on study.
- 18 Following evaluation of the safety data for the first 6 subjects enrolled in each treatment arm, the Safety Review Team (SRT) will determine if weekly clinical evaluation should continue for the duration of the study.
- 19 The EOT visit should be scheduled for approximately 30 days following discontinuation of all study treatment. For subjects that permanently discontinue all treatment prior to Week 25 Day 1, the Week 25 Day 1 visit should also be performed and may satisfy the requirement for the EOT visit if falling into the +30 days \pm 7 day window from all study drug discontinuation.

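### Does the Week 25 exception in SAP 1.2 alter the time to clinical response defined in SAP 6.4?

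*SAP*

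**What the plan says.** SAP 6.4 lists endpoints that the protocol does not define. One is time to clinical response, which runs from first dose to "the date of the first clinical response which includes clinical complete response (CCR) and clinical partial response (CPR". The same section describes the rating behind it as "performed every 4 weeks until Week 33 Day 1 and then at all scheduled visits thereafter following the modified IWCLL 2008 criteria". SAP 6.4.2 opens its formula with "Time to clinical response in months will be calculated by" and divides the inclusive number of days by 30.4375. The summary is descriptive, with a by-subject listing.

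The efficacy assessment schedule in SAP 1.2 places the same rating "every 4 weeks until Week 33 Day 1 (except for Week 25) and then every 12 weeks starting Week 33 until Week 105". It does not name EOT.

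Footnote 17 of SAP Appendix 1 has no Week 25 exception. After Week 33 it puts the rating "at all scheduled visits thereafter following the modified IWCLL 2008 criteria, with the exception of lymphadenopathy, hepatomegaly, splenomegaly, and bone marrow", and it adds: "Assessment of response per modified IWCLL 2008 criteria should also be recorded at the completion of 24 weeks on treatment". The Response Assessment row of that schedule is marked at Week 25 and at EOT. Footnote 17 of protocol Appendix 2 agrees with SAP Appendix 1.

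On-study ORR in SAP 6.4.1 is a separate endpoint, built on full IWCLL responses: "The analysis will be performed with data collected throughout the study".

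**The concern.** Two visit lists for one rating, in current and unredacted text, suggest that two programmers could obtain different answers from the same data. If SAP 1.2 governed, a first CCR or CPR at Week 25 would have to wait for Week 29. Footnote 17 makes the full IWCLL assessment additional to the clinical rating, so the Week 25 exception cannot simply be read as a replacement that the schedule supports. No visible sentence converts an IWCLL CR, CRi, PR or PR-L into a CCR or CPR.

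Some subjects would have no later rating at all. SAP 1.2 limits monitoring to 30 days after end of treatment, or "up to Week 25 should a subject discontinue treatment prior to Week 25 for reasons other than disease progression". Protocol 6.7 still brings a subject who stopped early without progression to the Week 25 visit, and footnote 19 of the schedule lets that visit serve as EOT if it falls in the window. Such a subject could count as a responder for on-study ORR and have no time to clinical response. At stake would be the dates, and the number of subjects, behind one added summary.

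**Working it through.** **Visit lists.**
- SAP 1.2: Weeks 5, 9, 13, 17, 21, 29 (6 visits) plus Weeks 33, 45, 57, 69, 81, 93, 105 (7 visits) = 13.
- SAP Appendix 1 row: the same 13 plus Week 25 and EOT = 15.

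**Dates.** The documents state no figure for this endpoint, so there is none to reproduce. SAP 3.8.1 makes the first dose study day 1, so Week w Day 1 is day 7(w − 1) + 1. SAP 6.4.2 gives months = (response date − first dose date + 1)/30.4375, which is study day/30.4375.
- Week 25 Day 1: 7 × 24 + 1 = 169; 169/30.4375 = 5.55 months (5.32 to 5.78 across ±7 days).
- Week 29 Day 1: 7 × 28 + 1 = 197; 197/30.4375 = 6.47 months (6.24 to 6.70 across ±7 days).
- Difference: 28/30.4375 = 0.92 months.

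**Effect on the mean.** With k subjects moved from Week 25 to Week 29 among r with an event, the mean shifts by 0.92 × k/r. The documents give neither k nor r, so these are assumptions:

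| k/r | Shift (months) | Shift (days, 28 × k/r) |
|---|---|---|
| 1/30 | 0.03 | 0.9 |
| 3/30 | 0.09 | 2.8 |
| 6/30 | 0.18 | 5.6 |
| 1/6 (Arm A) | 0.15 | 4.7 |

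The median moves, by at most 0.92 months, only if it falls at that visit.

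**Which text sets the event date.**
1. SAP 1.2 is a design summary. It says when ratings take place and gives no instruction to drop any.
2. SAP 6.4 defines the event as the first CCR or CPR, and SAP 6.4.2 uses its date. Neither restricts that date to a list of visits in the visible text.
3. SAP 3.8.3 notes that a time-to-event analysis does not need a single value per analysis window, so no windowing rule removes a Week 25 record.
4. If a CCR or CPR was recorded at Week 25, sections 6.4 and 6.4.2 date it there, nominally at 5.55 months. If none was collected, no wording supplies one, and 6.47 months applies only if the response is still present at Week 29.

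**Who could be affected.** Five ratings precede Week 25 (Weeks 5, 9, 13, 17, 21). A subject must miss CCR and CPR at all five and then first meet one of them at Week 25. The Week 25 scan does not create such cases, because the rating rests on examination, laboratory values and B-symptoms and does not use imaging. A first IWCLL response on the scan is a different event.

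**Would a missing subject show?** SAP 3 reports n for every continuous summary. By-subject listings are planned for overall response (SAP 6.2.2 and 6.4.1) and for time to clinical response (SAP 6.4.2). A subject in one and not the other can be identified from them.

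**The case for a change.** The strongest case for a change is that SAP 1.2 departs from the protocol schedule and the visible part of SAP 6.4, the place for such departures, does not say so. If the case report form followed SAP 1.2, an ORR responder could lack a clinical response time. An event sentence that also accepted IWCLL responses would close that gap without new data.

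The first part stands as a clerical inconsistency. The Week 25 exclusion is explicit. The EOT difference is weaker: SAP 1.2 is silent on EOT, and the wording in SAP 6.4 about visits after Week 33 does not clearly reach an EOT visit before Week 33, which only the schedule row covers.

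The remedy does not follow. SAP 6.4 keeps IWCLL response and clinical response as separate endpoints, and the title of SAP 6.4.2 ties the time to the clinical assessment. Adding CR, CRi, PR and PR-L to the event would mix scan-driven dates with clinical ratings. Unless the exclusion in SAP 6.4.1 for responses after other anti-cancer therapy were carried over, it would also give times to subjects whom ORR counts as nonresponders.

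A related ambiguity is that the rating uses physical examination yet excepts nodes, liver, spleen and marrow, and no CCR or CPR thresholds are visible. Parts of SAP 6.4 and 6.4.2 are blacked out, so their absence from the visible text cannot be held against the plan. The point concerns how the rating is described and does not affect which date is used.

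**Conclusion.** The Week 25 exception in SAP 1.2 is a clerical mismatch with SAP 6.4, SAP Appendix 1 and the protocol schedule. It does not govern the analysis. An analyst working from SAP 6.4 and 6.4.2 takes the earliest recorded CCR or CPR, whatever the visit, which is the sensible reading. Aligning the visit lists would be tidier but would change no result, and redefining the event would alter the endpoint without clear gain.

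The size is at most 0.92 months for a subject rated again at Week 29, and 0.03 to 0.18 months on the Arm B mean if 1 to 6 of 30 responders were affected. A subject with no later rating would lower n by one, which the planned n and listings would reveal. These figures assume visits on nominal days, response persisting to Week 29, and that no Week 25 clinical rating was collected. The case report form is not available to settle the last point. The Week 25 CR, MRD and ORR results and on-study ORR do not depend on it.

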6.4.1. ORR

The analysis will be performed with data collected throughout the study. Subjects, who never achieved these responses or received anti-cancer therapy other than the study drug prior to achieving responses, will be considered as nonresponders and will be included in the denominator when calculating ORR.

ORR and the corresponding 2-sided 90% exact CIs based on Clopper-Pearson method will be presented. A by-subject listing of overall response will be provided.

6.4.2. Time to Clinical Response **CCI** per Clinical Response Assessment

Time to clinical response in months will be calculated by $(\text{date of first clinical response} - \text{date of first dose of study drug} + 1) / 30.4375$.

Time to clinical response will be summarized using descriptive statistics. A by-subject listing of time to clinical response will be provided.

CCI
[REDACTED]

CCI

For missing or incomplete dates of new anti-cancer therapy and death, imputation rules are described in Sections [6.3.2](#) and [6.3.1](#), respectively.

CCI

7. SAFETY ANALYSES

7.1. Adverse Events and Deaths

7.1.1. Adverse Event Dictionary

Clinical and laboratory AEs will be coded using the current version of MedDRA. System organ class (SOC), high-level group term (HLGT), high-level term (HLT), preferred term (PT), and lower-level term (LLT) will be provided in the AE dataset.

7.1.2. Adverse Event Severity

Adverse events are graded by the investigator as Grade 1, 2, 3, 4, or 5 according to CTCAE Version 4.03. The severity grade of events for which the investigator did not record severity will be categorized as “missing” for tabular summaries and data listings. The missing category will be listed last in summary presentation.

7.1.3. Relationship of Adverse Events to Study Drug

Related AEs are those for which the investigator selected “Related” on the AE CRF to the question of “Related to Study Treatment GS-4059”, “Related to Study Treatment Idelalisib”, or “Related to Study Treatment Obinutuzumab”. Relatedness will always default to the investigator’s choice, not that of the medical monitor. Events for which the investigator did not record relationship to study drug will be considered related to study drug for summary purposes. However, by-subject data listings will show the relationship as missing.

7.1.4. Serious Adverse Events

Serious adverse events (SAEs) will be identified and captured as SAEs if the AEs met the definitions of SAEs that were specified in the study protocol. SAEs captured and stored in the clinical database will be reconciled with the SAE database from the Gilead Pharmacovigilance and Epidemiology Department before data finalization.

7.1.5. Treatment-Emergent Adverse Events

7.1.5.1. Definition of Treatment-Emergent Adverse Events

Treatment-emergent adverse events (TEAEs) are defined as 1 or both of the following:

- Any AEs with an onset date on or after the study drug start date and no later than 30 days after permanent discontinuation of study drug
- Any AEs leading to discontinuation of study drug

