6.2.10. Adverse Events

Subjects will be assessed for AEs per guidelines in the NCI CTCAE (version 4.03) at the time points outlined in the Study Procedures Tables ([Appendix 2](#)). After informed consent, but prior to initiation of study medication, the following types of events should be reported on the electronic case report form eCRF: AEs related to protocol-mandated procedures, and all SAEs.

Any AEs reported after informed consent is obtained and throughout the study will be recorded on the eCRF with appropriate source documentation. Please refer to [Appendix 3](#) for CTCAE grading criteria.

Please refer to Section [7](#) for additional information on AE reporting.

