7.2.2. Assessment of Severity

The severity of AEs will be recorded and graded according to the NCI CTCAE, Version 4.03, published 14 June 2010.

If a CTCAE criterion does not exist, the investigator should use the grade or adjectives: Grade 1 (mild), Grade 2 (moderate), Grade 3 (severe), Grade 4 (life-threatening), or Grade 5 (fatal) to describe the intensity of the AE. For purposes of consistency with the CTCAE, these intensity grades are defined in [Table 7-1](#).

Table 7-1. Grading of Adverse Event Severity

Grade	Adjective	Description
Grade 1	Mild	Sign or symptom is present, but it is easily tolerated, is not expected to have a clinically significant effect on the subject's overall health and well-being, does not interfere with the subject's usual function, and is not likely to require medical attention.
Grade 2	Moderate	Sign or symptom causes interference with usual activity or affect clinical status, and may require medical intervention.
Grade 3	Severe	Sign or symptom is incapacitating or significantly affects clinical status and likely requires medical intervention and/or close follow-up.
Grade 4	Life-threatening	Sign or symptom results in a potential threat to life.
Grade 5	Fatal	Sign or symptom results in death.

The distinction between the seriousness and the severity of an AE should be noted. Severe is a measure of intensity; thus, a severe reaction is not necessarily a serious reaction. For example, a headache may be severe in intensity, but would not be classified as serious unless it met 1 of the criteria for serious events listed in Section 7.1.2.

7.3. Investigator Requirements and Instructions for Reporting Adverse Events and Serious Adverse Events to Gilead

Requirements for collection prior to study drug initiation:

After informed consent, but prior to initiation of study medication, the following types of events should be reported on the eCRF: adverse events related to protocol-mandated procedures, and all SAEs.

Adverse Events

Following initiation of study medication, collect all AEs, regardless of cause or relationship, until 30 days after last administration of study IMP must be reported to the eCRF database as instructed.

All AEs should be followed up until resolution or until the adverse event is stable, if possible. Gilead Sciences may request that certain AEs be followed beyond the protocol defined follow up period.

Serious Adverse Events

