8.6.2. Adverse Events

Clinical and laboratory adverse events (AEs) will be coded using the current version of Medical Dictionary for Regulatory Activities (MedDRA). The severity of AEs will be graded according to the NCI-CTCAE, Version 4.03. The relationship of the AE to the study treatment will be assessed by the investigator as related or unrelated.

All AEs will be listed. The focus of AE summarization will be on treatment-emergent AEs (TEAEs). A TEAE is defined as an AE that occurs or worsens in severity on or after the date of the first dose of study treatment but no later than 30 days after the last dose of study treatment.

Summaries (number and percentage of subjects) of treatment-emergent adverse events (by SOC and PT) will be provided by treatment group:

- All TEAEs
- TEAEs of Grade 3 or above
- All treatment-related AEs
- Treatment-related AEs of Grade 3 or above
- All treatment-emergent SAEs
- All treatment-related SAEs
- All AEs leading to premature discontinuation of study drug
- All AEs leading to dose modification or temporary interruption of study drug
- All SAEs leading to death (ie, outcome of death)

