7.1.5.2. Incomplete Dates

If the onset date of the AE is incomplete and the AE stop date is not prior to the first dosing date of study drug, then the month and year (or year alone if month is not recorded) of onset determine whether an AE is treatment emergent. The event is considered treatment emergent if both of the following 2 criteria are met:

- The AE onset is the same as or after the month and year (or year) of the first dosing date of study drug, and
- The AE onset date is the same as or before the month and year (or year) of the date corresponding to 30 days after the date of the last dose of study drug

An AE with completely missing onset and stop dates, or with the onset date missing and a stop date later than the first dosing date of study drug, will be considered to be treatment emergent. In addition, an AE with the onset date missing and incomplete stop date with the same or later month and year (or year alone if month is not recorded) as the first dosing date of study drug will be considered treatment emergent.

In case when the AE onset date is incomplete and needs to be imputed, the following algorithm will be followed:

- If the day is missing but the month and year are available, then the imputed day will be the first day of the month or the first dosing date if they have the same month and year, whichever is later.
- If the day and month are missing but year is available, then the imputed day and month will be 01Jan or the first dosing date if they have the same year, whichever is later.

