7.7. Changes From Protocol-Specified Safety Analyses

There are no deviations from the protocol-specified safety analyses.

CC [REDACTED]

[REDACTED]

[REDACTED]

[REDACTED]

[REDACTED]

[REDACTED]

[REDACTED]

[REDACTED]

[REDACTED]

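### The SAP's TEAE definition omits on-treatment worsening and adds a discontinuation criterion, yet SAP 7.7 declares no change from the protocol

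*SAP*

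**What the plan says.** Protocol 8.6.2 has two triggers: "A TEAE is defined as an AE that occurs or worsens in severity on or after the date of the first dose". Its window closes 30 days after the last dose of study treatment.

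SAP 7.1.5.1 also has two limbs, and either is sufficient. The first concerns onset only: "Any AEs with an onset date on or after the study drug start date and no later than 30 days after permanent discontinuation". The second carries no dates: "Any AEs leading to discontinuation of study drug". Worsening appears in neither.

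SAP 7.1.5.2, for incomplete dates, again works from onset. The first of its two conditions is "The AE onset is the same as or after the month and year (or year) of the first dosing date of study drug".

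SAP 7.7 then says: "There are no deviations from the protocol-specified safety analyses". The revision table in SAP 11 lists no change to 7.1.5.

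On what is collected before first dose, Protocol 7.3 says "the following types of events should be reported on the eCRF: adverse events related to protocol-mandated procedures, and all SAEs". Protocol 6.2.10 gives the same restriction and follows it with a wider sentence: "Any AEs reported after informed consent is obtained and throughout the study will be recorded on the eCRF".

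**The concern.** The two definitions classify some events differently, and the SAP section meant for declaring such differences says there are none. Type, frequency and severity of AEs and SAEs is a secondary endpoint (Protocol 8.1.3), and the AE incidence tables in SAP 7.1.6.1 and 7.1.7 rest on the TEAE definition. If an event that began in screening becomes more severe on treatment, the protocol counts it and the SAP may not.

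Disclosure is also at stake. SAP 1 commits to documenting in the study report only those changes made after the SAP is final. This difference is already in the SAP, so nothing in the plan ensures that a reader of the report learns of it. The sponsor did use the efficacy counterpart, SAP 6.4, to declare added endpoints.

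**Working it through.** No rate can be computed, because the documents give no count of affected events. The check is a side-by-side classification.

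| Event | Protocol 8.6.2 | SAP 7.1.5.1 |
|---|---|---|
| (a) Starts after consent and before first dose; worsens on treatment; same record and original onset date; no drug stopped | TEAE | Not a TEAE |
| (b) As (a), but the worsening is entered as a new record with its own onset date | TEAE | TEAE (onset limb) |
| (c) As (a), but it leads to drug discontinuation | TEAE | TEAE (discontinuation limb) |
| (d) Starts before first dose; does not worsen; leads to drug discontinuation | Not a TEAE | TEAE (discontinuation limb) |
| (e) Starts between first dose and 30 days after last dose | TEAE | TEAE |
| (f) Leads to discontinuation; starts more than 30 days after last dose | Not a TEAE | TEAE, but outside routine AE collection (Protocol 7.3) |

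The definitions therefore differ in both directions. Only (a) is a loss. Rows (d) and (f) are additions, and (f) is hardly realistic, so in practice the added limb brings in events that began before first dose.

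**How wide row (a) is.** Onset must fall between consent and first dose, for which Protocol 6.2.1 gives a screening window of 28 days. On the Protocol 7.3 reading only two kinds of event are recorded then: procedure-related AEs and SAEs. The wider sentence in Protocol 6.2.10 would admit more. Conditions that began before consent, unless related to a study procedure, go to medical history under Protocol 7.1.1. If one worsens on treatment, the AE itself is new and the onset limb catches it.

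**Which tables could be touched.** The categories in SAP 7.1.6.1 are: all TEAEs 1, Grade 3 or higher 1, related 3, related and Grade 3 or higher 3, serious 1, related serious 3, drug discontinuation 3, dose modification 3, interruption 3, study discontinuation 1, death 1.

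1 + 1 + 3 + 3 + 1 + 3 + 3 + 3 + 3 + 1 + 1 = 23

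The 3 drug-discontinuation categories cannot lose an event, because the second limb holds it: 23 − 3 = 20. These 20 are the categories in which a loss is possible, not ones known to change. A subject counts once per summary, so a row changes only if that subject has no other qualifying event in it.

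**The case against.** The strongest reply is that row (a) may be empty. Protocol 7.1.1 says that a pre-existing event which increases in severity is itself an AE. If sites give that AE its own record and date, the onset limb captures it and the SAP loses nothing. Protocol 7.3 refers recording detail to eCRF instructions and completion guidelines, which are not among the documents. This stands as a reason to expect a small effect. It does not remove the conflict, because neither document says that a worsening receives a new record or a new onset date.

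Other safeguards also count:

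- An excluded event still appears in the listing of all AEs, which shows whether each is treatment-emergent, and in the Grade 3 or higher and SAE listings where it qualifies.
- Laboratory worsening is summarised separately: a rise of at least one grade from baseline (SAP 7.2.2.1) and shift tables (SAP 7.2.4).
- All deaths are tabulated whatever their TEAE status (SAP 7.1.6.1.1).
- The safety analysis is descriptive, with no comparison between arms intended.

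These limit the consequence. The laboratory rules do not cover clinical AEs, and none of these safeguards makes SAP 7.7 correct.

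On the discontinuation limb the objection succeeds almost fully. It cannot remove an event, its missing dates matter little because routine AE collection ends 30 days after last dose, and Protocol 8.6.2 already tabulates AEs leading to discontinuation.

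**Conclusion.** The concern holds as a minor but genuine conflict. SAP 7.1.5.1 and 7.1.5.2 omit a criterion that Protocol 8.6.2 includes, SAP 7.1.5.1 adds one that the protocol lacks, and SAP 7.7 wrongly states that nothing differs. This part rests on the text alone and needs no assumption.

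Any effect on results requires three things together: onset between consent and first dose, worsening kept under the original record, and no drug discontinuation. The number of such events is unknown, probably small and possibly zero.

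A reader might infer that TEAE rates will be understated across 20 of the 23 categories, or that the undated limb distorts them in the other direction. The documents support neither reading. The figure of 20 counts tables that use the definition without the protection of the second limb; it is not evidence that any entry moves. The added limb is faulty only in being undeclared.

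**What to change.** 1. **SAP 7.1.5.1.** Restore worsening and use one window throughout, for example: *an AE is treatment-emergent if it starts or becomes more severe between the first dose and 30 days after the last dose of study treatment, or if it leads to discontinuation of a study drug.* Where a worsening is not a new record, classify by the date of worsening. The single window also removes a mismatch inside the SAP, where 7.1.5.1 counts from permanent discontinuation and 7.1.5.2 from last dose.
2. **SAP 7.1.5.2.** Apply the same wording to incomplete dates, so that a partial date of worsening has a rule.
3. **SAP 7.7.** Replace the no-deviation statement with a declaration of the discontinuation criterion.

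Alternatively, if the sponsor keeps the onset-only rule because a worsening is always entered as a new AE record, SAP 7.1.5.1 should say so and SAP 7.7 should declare both differences.

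The cost is a few sentences and no new tables. If the eCRF does not hold a date of worsening, the few AEs with onset before first dose may need queries. Some TEAE rates may rise slightly.
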